## DOCUMENT HISTORY

Document	Date of Issue	Summary of Change
Revised Protocol 04	02-Nov-2016	Incorporates Amendment 06
Amendment 06	02-Nov-2016	Added additional echocardiogram to cycle 2 for Part 3 (nivolumab combination treatment arm). Clarification of dosing administration (line flush between doses of BMS986148 and nivolumab) in Part 3.
Revised Protocol 03	21-Jul-2016	Incorporates Amendment 03
Amendment 05	21-Jul-2016	Removed flat dosing option. Added BMS-986148 and nivolumab combination therapy arm (Part 3). [REDACTED] Corrected typographical and consistency errors.
Revised Protocol Number 02a - UK	19-May-2016	Incorporates Amendment 04
Amendment 04	19-May-2016	Incorporate changes [REDACTED] [REDACTED] regarding use of contraceptives
Revised Protocol Number 02a - US	12-Apr-2016	Incorporates Amendment 03
Amendment 03	12-Apr-2016	Refined eligibility criteria [REDACTED]
Revised Protocol 02	02-Feb-2016	Incorporates Amendment 02
Amendment 02	02-Feb-2016	Added details for flat dosing, Added IHC scoring details for Part 2 of the study. Clarified eligibility criteria and corrected typographical errors.
Revised Protocol 01	31-Jul-2015	Incorporates Amendment 01
Amendment 01	31-Jul-2015	Incorporates [REDACTED] revisions regarding additional on-treatment echocardiograms, DLT definitions, and dose selection for Part 2. Enhanced the survival period duration of follow-up and alignment of the survival period with other early development protocols. Added additional detail to DLT criteria. Added exclusion criteria for troponin. Added additional guidance on the collection of triplicate ECGs. Modified text for clarity. Added windows for the collection on eye exams and laboratory collections. Added C1D15 vital signs and targeted PE to Q weekly dosing. Added wording to footnote in PK collection tables. Addresses typographical errors
Original Protocol	28-Nov-2014	Not applicable

## SYNOPSIS

### Clinical Protocol CA008002

**Protocol Title:** A Phase 1/2a Study of BMS 986148, a Mesothelin-Directed Antibody Drug Conjugate, in Subjects with Select Advanced Solid Tumors

**Investigational Product(s), Dose and Mode of Administration, with Investigational Product(s):** Each subject will be administered intravenous doses of BMS-986148 or BMS-986148 and nivolumab per the cohort assignment as indicated in the study design below (See [Figure 1](#) and [Figure 2](#) in the synopsis).

[figure not shown]
**Study Phase:** 1/2a

**Research Hypothesis:** There is no formal primary research hypothesis for this study to be statistically tested. The purpose of this study is to evaluate the safety profile, tolerability, preliminary efficacy, pharmacokinetics (PK), and pharmacodynamics (PD) of BMS-986148 administered alone and in combination with nivolumab in subjects with select advanced solid tumors.

**Primary Objectives:** To assess the safety and tolerability of BMS-986148 administered as monotherapy and in combination with nivolumab in subjects with select advanced solid tumors.

[figure not shown]
**Secondary Objectives:**

- To assess the preliminary anti-tumor activity of BMS-986148 as monotherapy and in combination with nivolumab as measured by objective response rate (ORR), response duration, and progression-free survival (PFS)
- To characterize the PK of the total antibody (unconjugated antibody + antibody conjugated to tubulysin or antibody conjugated to any tubulysin metabolites), active anti-drug conjugate (ADC, antibody conjugated to tubulysin), and unconjugated tubulysin when BMS-986148 is administered as monotherapy and in combination with nivolumab
- To characterize the PK of nivolumab when administered in combination with BMS-986148
- To assess the effect of BMS-986148 monotherapy dosage regimen and exposure (active ADC and unconjugated tubulysin) on the QT interval
- To characterize the immunogenicity of BMS-986148 as monotherapy and in combination with nivolumab
- To characterize the immunogenicity of nivolumab in combination with BMS-986148

[figure not shown]

**Study Design:** This is a Phase 1/2a, open-label study to characterize the safety and tolerability, as well as preliminary efficacy, PK, and PD of BMS-986148 administered alone and in combination with nivolumab in subjects with select advanced solid tumors (pancreatic, ovarian, non-small cell lung cancer [NSCLC], gastric, or mesothelioma). The study has 3 segments: Part 1 (Phase 1 study - dose escalation), Part 2 (Phase 2a - dose expansion), and Part 3 (BMS-986148 in combination with nivolumab; Part 3A - dose escalation and Part 3B - dose expansion) (see Figure 1). All subjects will complete up to 4 study periods: Screening (up to 28 days), Treatment (21 days/cycle for Q3W dosing and 28 days/cycle for QW dosing), Follow-up (60 days), and Survival Follow-up. After completing the Follow-up period, subjects will continue to be followed for [REDACTED] up to 2 years from first dose of study drug for subjects discontinuing study drug prior to 2 years. Subjects receiving study drug for more than 2 years, will be followed for 6 months from their last treatment date in the Survival Follow up Period (see Figure 2). With Amendment 3, a dose escalation phase will be conducted with BMS-986148 and nivolumab combination therapy (Part 3A). In the BMS-986148 and nivolumab combination therapy dose expansion phase (Part 3B), additional subjects with pancreatic, ovarian, NSCLC, gastric, or mesothelioma will be treated at or below the maximum tolerated dose (MTD) of the combination dose identified in Part 3A to confirm safety and evaluate anti-tumor activity.

**Figure 1: Sequence of Study Phases**

**Figure 2: Dosing (Q3W and QW) and Study Periods**

Note: Subjects treated for > 2 years will be followed for 6 months after EOT in the Survival Follow-Up. In the Survival Follow-up, subjects discontinuing study drug prior to 2 years will be followed for up to 2 years from first dose of study drug. Additionally, specifically in Part 3, treatment duration is 24 weeks to a maximum of 48 weeks.

C1D1: Cycle 1 Day 1 (first dose); D: day; DLT: dose-limiting toxicity; EOT: end of treatment; QW: every week; Q3W: every 3 weeks.

**Part 1A: BMS-986148 Administered Every 3 Weeks**

Approximately 30 subjects will be enrolled in ascending dose cohorts starting with a dose of 0.1 mg/kg. BMS-986148 will be administered Q3W in a 21-day cycle. The approach for selection of the next dose at each escalation step (including Fibonacci and modified Fibonacci methods) and the rules for escalation decision based on dose limiting toxicity (DLT) criteria guided by the modified Toxicity Probability Interval (mTPI) design are described in Section 3.1.1 of the protocol, with the dose escalation design described in Figure 3.1.1-1 of the protocol.

At the end of dose escalation, the MTD will be selected as the dose with the smaller difference of estimated toxicity and the target DLT rate (27%), among the doses used, with isotonic regression modeling of the accumulated DLT data based on the mTPI design.

**Part 1B: BMS-986148 Administered Weekly for 3 Weeks and 1 Week Off**

Approximately 24 subjects will be enrolled in ascending dose cohorts. Part 1B may begin after determining the MTD or a tolerated dose below the MTD in Part 1A. The starting dose for Part 1B will be chosen by modeling active ADC concentration-time data from Part 1A and selecting a fractionated dose that provides similar exposure to that of the MTD or a tolerated dose below the MTD. In the event that concentration-time data are not available for modeling, the starting dose will be 1/3rd of the MTD or a tolerated dose below the MTD from Part 1A. In Part 1B, BMS-986148 is administered every week for 3 weeks and 1 week off in a 28 day cycle. Similar to Part 1A, the approach for selection of the next dose at each escalation step (including Fibonacci and modified Fibonacci) and the rules for escalation decision based on DLT criteria guided by the mTPI design are described in Section 3.1.1 of the protocol, with the dose escalation design described in Figure 3.1.1-1 of the protocol.

Similar to the MTD determination in Part 1A, at the end of dose escalation, the MTD will be selected as the dose with the smaller difference of estimated toxicity and the target DLT rate (27%), among the doses used.

Once the safety (during DLT evaluation) of a dose level has been established (Part 1A and/or Part 1B), additional subjects may be added at that dose to better characterize the PK, safety, and PD profile.

### Part 2: Monotherapy Dose Expansion

The purpose of the cohort expansion will be to assess preliminary antitumor efficacy, expanded safety experience and PD effects of BMS-986148. Additional subjects will be treated after the completion of Part 1A and/or Part 1B, at the MTD, or at an alternative dose below MTD as agreed upon by the BMS Medical Monitor and investigators. Part 2 can begin before the completion of Part 1B as the Q3W dosing regimen is the intended regimen for Part 2. However, if the aggregate PK and safety data indicate similar safety but higher cumulative exposure with the weekly dose schedule, this schedule may also be evaluated in Part 2 in an additional cohort of 25 to 26 subjects, once the MTD or a tolerated dose below the MTD is identified in Part 1B. Treatment doses in the cohort expansion groups will not exceed the MTD.

Five expansion cohorts will be restricted to these tumor types 1) mesothelioma 2) pancreatic 3) ovarian 4) NSCLC, and 5) gastric cancer. Enrollment in cohort expansion will be determined by the mesothelin expression of an archived tumor sample (or fresh tumor sample if archived sample is not available).

The enrollment in each expansion cohort will be guided by a Simon 2-Stage design framework exploring the efficacy in the following 2 populations:

Safety monitoring of subjects enrolled in the Part 2 (Phase 2a) portion of the study will be the same as that conducted during the dose escalation portion. During Part 2, if in a given arm the combined incidence of study drug-related AEs that require dose modification exceeds 29% (of treated subjects), then further enrollment to that arm will be interrupted and the findings will be discussed between the BMS Medical Monitor and investigators. An agreement will be reached as to whether a lower dose or an alternate dose schedule of BMS-986148 should be examined or whether any additional treatment guidelines should be implemented prior to enrollment of additional subjects on study.

### Part 3: BMS-986012 in Combination with Nivolumab

During the dose escalation phase with BMS-986148 and nivolumab combination therapy (Part 3A), approximately 12 evaluable subjects are expected to be treated at 2 doses of BMS-986148 (0.8 mg/kg Q3W and 1.2 mg/kg Q3W) and nivolumab (360mg, Q3W) combination therapy (21 day cycle). In the BMS-986148 and nivolumab combination therapy dose expansion phase (Part 3B), approximately 25 to 26 evaluable subjects will be treated in each tumor cohort.

Subsequent escalation to 1.2 mg/kg Q3W of BMS-986148 (or MTD determined from Part 1A) in combination with nivolumab 360 mg Q3W will be guided by the mTPI design described in Section 3.1.3 of the protocol. In the event that the first dose level of BMS-986148 is determined to exceed the MTD in combination with 360 mg Q3W of nivolumab, a lower BMS-986148 dose may be explored based on available safety, PK. Nivolumab will be administered as 360 mg IV Q3W in all the dose cohorts. Dose escalation decisions are similar to Part 1A and described in Figure 3.1.1-1 of the protocol. A DLT target rate of 29% (EI = 28% to 31%) will be utilized for combination treatment to guide escalation decisions. Dose escalation decisions will be based on the total number of subjects in a dose level who were DLT evaluable and the number of DLTs, guided by the mTPI Bayesian model and posterior inference.

Similar to the MTD determination in monotherapy parts, at the end of dose escalation, the cumulative number of subjects who experience a DLT at each dose level will be used to estimate the MTD using isotonic regression as the dose with the smaller difference of estimated toxicity rate and the target DLT rate (29%), among the doses used.

Once the safety (during DLT evaluation) of a dose level has been determined, additional subjects may be added at that dose, to better characterize the PK, safety, and PD profile.

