Decisions to escalate, add more subjects to the current dose, de-escalate, or de-escalate and declare the current dose as unacceptable (exceeding the MTD), will be based on the rate of DLTs in evaluable subjects within the 21-day DLT evaluation period for Part 1A guided by the mTPI model and posterior inference (Figure 3.1.1-1 and Appendix 1). At least 2 DLT-evaluable subjects treated at each of the lowest 2 dose levels and at least 3 DLT-evaluated subjects treated at each of the other dose levels are required to enable decision making. Subjects with insufficient data to establish safety during the DLT evaluation period at the dose tested (eg, omitted or reduced doses for reasons other than a DLT) may be replaced upon agreement of the BMS Medical Monitor and investigators.

[figure not shown]
In addition, if dose modifications for ocular toxicity occur in 2 or more subjects within the first 5 subjects treated on study, or if with greater patient numbers > 20% of subjects require a dose modification due to ocular toxicity, enrollment will be suspended at all dose levels equal to or greater than the lowest dose level with a dose modification due to ocular toxicity, in order to assess the safety data. Enrollment may continue at lower dose levels where no dose modifications have occurred due to ocular toxicity while this safety assessment is being conducted.

There will be no intrasubject dose escalation of BMS-986148.

Figure 3.1.1-1 shows examples of scenarios guiding decision making that may be encountered during dose escalation with respect to the number of DLT evaluable subjects and the number of subjects with a DLT. All potential combinations of the number of DLTs and number of treated subjects evaluable for DLT are shown in Appendix 1. In addition to escalation or expansion decisions, dose re-escalation is permitted as per Figure 3.1.1-1 and Appendix 1 after a decision to de-escalate is made, except when a dose has been identified as exceeding the MTD. Therefore, a dose level could be revisited multiple times under the mTPI design.

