**Figure 3.1.1-1: Dose Escalation Algorithm**

a Treat 2 subjects initially if no DLTs in Dose Level 1 and criteria for transitioning from 100% increment to Fibonacci is not met; treat 3 to 4 subjects initially, otherwise.

b At the same dose, decision making based on other combinations of k/n are shown in [Appendix 1](#).

c Treat the next cohort of subjects at the next higher dose.

d Treat 3 more subjects at the current dose.

e Treat 3 more subjects at the next lower dose.

f Unacceptable current dose. Do not re-escalate to this dose.

DLT: dose-limiting toxicity; k: cumulative number of subjects who experienced DLT; MTD: maximum tolerated dose; n: cumulative number of DLT evaluable subjects; QW: every week; Q3W: every 3 weeks.

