### **Part 1B: Dose Escalation Decision Rules**

The same mTPI design (Figure 3.1.1-1 and Appendix 1) as in Part 1A will be used to help guide escalation decisions except that all dose levels in Part 1B begin with an initial number of 3 to 4 subjects. A fourth subject may be enrolled in a dose escalation cohort following agreement between the investigator and the BMS Medical Monitor if able to start the first day of dosing within approximately 1 week of the third subject in the same dose escalation cohort. The DLT evaluation period will be 28 days. At least 3 DLT-evaluable subjects treated at each of the dose levels in Part 1B will be required to enable a decision to escalate, add more subjects to the current dose level, or de-escalate. Subjects must receive 3 doses in Part 1B during the DLT evaluation period (unless DLT has occurred) to be considered evaluable for dose escalation decisions. Subjects with insufficient data to establish safety during the DLT evaluation period at the dose tested (eg, omitted or reduced doses for reasons other than a DLT) may be replaced upon agreement of the BMS Medical Monitor and investigators.

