### **3.1.3 BMS-986148 in Combination with Nivolumab (Part 3)**

During the dose escalation phase with BMS-986148 and nivolumab combination therapy (Part 3A), approximately 12 evaluable subjects are expected to be treated at 2 doses of BMS-986148 (0.8 mg/kg and 1.2 mg/kg Q3W) and nivolumab (360 mg Q3W) combination therapy. In the BMS-986148 and nivolumab combination therapy dose expansion phase (Part 3B), approximately 25 to 26 evaluable subjects will be treated at each tumor cohort.

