##### **Dose Escalation Decision Rules**

A similar mTPI design as in Part 1A will be used to guide dose escalation decisions and to select the MTD. A DLT target rate of 29% (EI = 28% to 31%) will be utilized for combination treatment to guide escalation decisions. Dose escalation decisions will be based on the total number of subjects in a dose level who were DLT evaluable and the number of DLTs, guided by the mTPI Bayesian model and posterior inference.

The number of subjects at the initial cohort of all dose levels in Part 3A will be 3 to 4. A fourth subject may be enrolled in a dose escalation cohort following agreement between the investigator and the BMS Medical Monitor if able to start the first day of dosing within approximately

1 week of the third subject in the same dose escalation cohort. The DLT evaluation period will be 21 days. Enrollment of additional cohorts at the same dose level will proceed in sample sizes of up to 3 or 4 subjects. Subsequent dose levels will follow similar cohort enrollment size and decision rules. At least 3 DLT-evaluable subjects treated at each of the dose levels in Part 3A will be required to enable a decision to escalate, add more subjects to the current dose level, or de-escalate and declare the current dose as unacceptable (exceeding the MTD). Subjects with insufficient data to establish safety during the DLT evaluation period at the dose tested (eg, omitted or reduced doses for reasons other than a DLT) may be replaced upon agreement of the BMS Medical Monitor and investigators.

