**Table 3.1.3.1-1: Dose Escalation Decision Guide in Combination with Nivolumab**

		Number of DLT Evaluable Subjects at a Dose Level									
		3	4	5	6	7	8	9	10	11	12
N of DLT at a dose level	0	E	E	E	E	E	E	E	E	E	E
	1	S	S	S	E	E	E	E	E	E	E
	2	D	S	S	E	S	S	S	S	E	E
	3	DU	DU	D	E	S	S	S	S	S	S
	4		DU	DU	DU	D	D	S	S	S	S
	5			DU	DU	DU	DU	DU	D	S	S
	6				DU	DU	DU	DU	DU	DU	D
	7					DU	DU	DU	DU	DU	DU
	8						DU	DU	DU	DU	DU
	9							DU	DU	DU	DU
	10								DU	DU	DU
	11									DU	DU
12										DU	

DLT: dose-limiting toxicity; E: escalate to next higher dose level; D: de-escalate to the next lower dose level; S: stay at the current dose level; DU: unacceptable dose level, not to be re-visited.

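### The synopsis refers Part 3A escalation decisions to Figure 3.1.1-1 (the Part 1 algorithm, tied to the 27% monotherapy table) instead of Part 3A's own 29% decision table, Table 3.1.3.1-1

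*Protocol*

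**What the plan says.** In the protocol synopsis, the Part 3 paragraph gives two pointers for Part 3A escalation. The step to 1.2 mg/kg "will be guided by the mTPI design described in Section 3.1.3 of the protocol". A little later it adds: "Dose escalation decisions are similar to Part 1A and described in Figure 3.1.1-1 of the protocol". The next sentence sets the combination target DLT rate at 29%, with an equivalence interval of 28% to 31%.

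Figure 3.1.1-1 sits in Section 3.1.1, Dose Escalation (Part 1). Its footnote b says that "decision making based on other combinations of k/n are shown in" Appendix 1. The Part 1A decision rules cite the figure and Appendix 1 together, and so do the Part 1B rules: "The same mTPI design (Figure 3.1.1-1 and Appendix 1) as in Part 1A will be used to help guide escalation decisions". Appendix 1 is titled for monotherapy, and its table is footnoted with a target of 27% plus or minus 2%.

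In Section 3.1.3.1, the decision rules repeat the combination target: "A DLT target rate of 29% (EI = 28% to 31%) will be utilized for combination treatment to guide escalation decisions". The table that follows, Table 3.1.3.1-1, is titled "Dose Escalation Decision Guide in Combination with Nivolumab". The decision-rules text does not cite that table by number, and it does not cite Figure 3.1.1-1. Section 8.1 also gives 29% (28% to 31%) for Part 3A. The SAP describes only Parts 1 and 2, so it does not settle the matter.

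**The concern.** The synopsis states a 29% design and then says the decisions are described in a figure that belongs to the 27% design. A dose-decision rule should have one source. The two sources prescribe different actions at sample sizes Part 3A will reach, because its cohorts start at 3 to 4 subjects and are extended by up to 3 or 4. A site or medical monitor who followed the synopsis pointer through to Appendix 1 would leave a dose at 2 DLTs in 4 where the combination table says to stay. At 1 in 6 they would repeat a dose where the combination table says to escalate. Because the decision-rules text never names Table 3.1.3.1-1, the synopsis figure is the only decision exhibit cited by number for Part 3A in the design text, which makes the slip easier to follow.

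**Working it through.** **Inputs.** Monotherapy: target 27%, interval 25% to 29% (Section 3.1.1; Appendix 1). Combination: target 29%, interval 28% to 31% (synopsis; Sections 3.1.3.1 and 8.1). Initial cohorts of 3 to 4 (Section 3.1.3.1). Size: "approximately 12 evaluable subjects are expected to be treated at 2 doses of BMS-986148" (Section 3.1.3). Assumed, because the documents do not state them: a Beta(1,1) prior, and DU when the decision is D and P(p > target) exceeds 0.95.

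**Formula.** With x DLTs in n subjects, the posterior is Beta(1 + x, 1 + n − x) with distribution function F. For an interval from lo to hi, the unit probability masses are E = F(lo)/lo, S = [F(hi) − F(lo)]/(hi − lo) and D = [1 − F(hi)]/(1 − hi). The largest decides.

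**Reproducing the plan's tables, n = 3 to 12 (85 cells each).** The 27% rule reproduces all 85 cells of Appendix 1. The 29% rule reproduces 83 of the 85 cells of Table 3.1.3.1-1. The exceptions are 2/6 and 3/6, which read E in the extracted text and compute as S.

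**Masses (E / S / D) at four cells.**

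| DLTs/n | 27% (25–29) | 29% (28–31) |
|---|---|---|
| 2/4 | 0.414 / 1.165 / 1.197 → D | 0.492 / 1.297 / 1.193 → S |
| 1/6 | 2.220 / 2.349 / 0.494 → S | 2.238 / 2.157 / 0.447 → E |
| 2/6 | 0.974 / 2.169 / 0.943 → S | 1.100 / 2.255 / 0.905 → S |
| 3/6 | 0.282 / 1.072 / 1.249 → D | 0.363 / 1.259 / 1.247 → S |

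**Differing cells, recomputed against recomputed (27% versus 29%): 10.**
- D versus S: 2/4, 3/6, 5/11.
- S versus E: 1/6, 2/11, 2/12.
- DU versus D: 3/5, 4/7, 5/10, 6/12.

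The tables as extracted differ in 11 cells: 2/6 joins the list (S versus E) and 3/6 becomes D versus E. The cells 2/4 and 1/6 differ on either reading. In every differing cell the monotherapy table is the more cautious.

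**How often a differing cell would be met, if the wrong table were used.**
- First cohort of four: 2/4 is the only differing cell at n = 4. At a true DLT rate of 29%, P(2/4) = 6 × 0.29² × 0.71² = 0.254. At 20% it is 0.154, and at 40% it is 0.346.
- Cohorts of three: nothing differs at n = 3, and 1/3 is the only stay cell there. So P(k/6) = P(1 of 3) × P(k − 1 of 3). At 29%, P(1 of 3) = 3 × 0.29 × 0.71² = 0.439. Then P(1/6) = 0.439 × 0.358 = 0.157 and P(3/6) = 0.439 × 0.179 = 0.079. The sum is 0.236, about 24%. Over true rates of 15% to 40% it runs from 22% to 24%.

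**The case against.** The best defence is that the paragraph corrects itself. It sends the reader to Section 3.1.3 and gives 29% immediately after the disputed sentence, and Appendix 1 is plainly labelled monotherapy. The protocol also uses the word same for Part 1B but similar for Part 3A, so the figure can be read as showing the escalate, stay and de-escalate scheme with Part 3A's own target put in. This largely stands as a reason for low severity. It does not make the pointer right: Part 3A's decisions are not described in the Part 1 figure, and a table in Section 3.1.3.1 does describe them.

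A second objection is that the comparison uses Appendix 1, which the synopsis sentence does not name. The figure image is not in the text available for review, and Section 3.1.1 says the figure shows example scenarios. Whether 2/4 or any other differing cell appears in it is unknown, so the link to 27% is indirect, through footnote b and the Part 1 text. That stands.

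Several differing cells are also remote or mild. Five (5/10, 2/11, 5/11, 2/12, 6/12) need at least 10 of about 12 planned subjects at one of two doses. At 3/5 and 4/7 both tables de-escalate at once and differ only on whether the dose may be revisited. The 1/6 difference matters mainly at 0.8 mg/kg, since 1.2 mg/kg is the higher planned dose. All of this stands too.

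**Conclusion.** The synopsis cross-reference is wrong and should be corrected, but the defect is small. The supported statement is 10 differing cells for n = 3 to 12 under the assumed prior and cut-off, including 2/4 and 1/6. The chances of meeting one at a true 29% DLT rate are about 25% (2/4 in a first cohort of four) and about 24% (by six subjects in cohorts of three). These are conditional on someone using the monotherapy table. The documents give no basis for saying how likely that is, and the figures are not probabilities of harm.

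Three stronger readings are not supported:
- A reader might infer that Part 3A would run at 27%. The synopsis paragraph, Section 3.1.3.1 and Section 8.1 all say 29%.
- A reader might infer added risk to subjects from the pointer. The monotherapy table is the more cautious in every differing cell, so following it would more plausibly cost efficiency.
- A reader comparing the extracted tables might report 11 differing cells and a 43% chance of discordance by six subjects (0.157 + 0.192 + 0.079 = 0.428), or say that the combination table escalates at 3 DLTs in 6. Those rest on the E entries at 2/6 and 3/6. The three-DLT row then runs D, E, S at n = 5, 6, 7, which does not fit the algorithm and may be a fault of text extraction. It cannot be called an error in the plan without the source page.

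**What to change.** In the synopsis Part 3 paragraph, replace the reference to Figure 3.1.1-1 with Table 3.1.3.1-1, and cite that table by number in the decision-rules text of Section 3.1.3.1. Before redirecting readers, check the six-subject column of Table 3.1.3.1-1 against the source document and the 29% (28% to 31%) algorithm. If 2/6 and 3/6 are really printed as E, correct both to S. Otherwise the new pointer would lead readers to a table that escalates at an observed DLT rate of 50%. The cost is two reference edits and a check of one table column, with no new data and no change to the design or the number of subjects.
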